6.1.2.2. Analysis of Covariance with Multiple Imputed data

An ANCOVA model will be used as a sensitivity analysis. For patients with missing Week 12 assessment due to any reason, the Week 12 value will be imputed using multiple imputation (see Appendix 11.1 for further details). The model will include terms for treatment, baseline value of the parameter, region (US vs. non-US), and stratification factors as randomized: alpha blocker use (with vs. without 5-ARI), baseline urinary incontinence (yes vs. no), baseline number of average daily micturition episodes (≤ 12 vs. > 12 , only included for the urgency parameter). The analysis will be performed on FAS and PP analysis sets.

An example of the SAS code for the base procedure is given below:

```
proc mixed data = datain method = reml;
  class TRTP ALPHAB UI REGION;
  model CHG = TRTP AVISITN ALPHAB UI REGION BASE
    / ddfm=KR solution chisq;
  Where AVISIT = "Week 12";
  lsmeans TRTP/ pdiff cl alpha=0.05;
run;
```

A tipping point analysis will accompany the multiply imputed ANCOVA results, and the estimated shift parameter will be presented to two decimal places.

The normality assumptions for the ANCOVA analysis model will be assessed by inspection of the residuals from the model and normal probability plots. If assumptions of normality are not met, additional supportive analysis of the data will be performed in order to assess the robustness of the conclusions drawn from the primary analysis.

This supportive analysis will use the multiple imputation (MI) data at Week 12 using a non-parametric analysis of covariance within the framework of the extended Cochran-Mantel-Haenszel test. Specifically, a Cochran-Mantel Haenszel mean score test will be used on the standardized mid-ranks of the residuals from an ordinary least squares regression with Week 12 MI response as a linear function of the baseline score (as a continuous variable). P-value for the between treatment comparison for each primary endpoint will be derived for the model.

This methodology will be carried out as follows:

1. The observed value of the primary endpoint (i.e., the last on treatment average number of daily micturition episodes) will be fitted using an ordinary least squares regression as a function of the baseline value at each visit
2. Standardized mid-ranks of the residuals from the regression will be calculated.
3. The standardized mid-rank from the last observation will be carried forward for missing values at week 12

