4. Standardized mid-ranks will be recalculated
5. A CMH mean score statistic and p-value adjusting for the stratification groupings will be calculated for between treatment comparisons

An example of the SAS code for the base procedure is given below:

```

proc glm Data=datain;
  by Avisitn;
  model aval = Base;
  output out=glmout residual=Residual;
run;

proc rank data=glmout out=Rank1 nplus1 ties=mean;
  by Avisitn;
  var Residual;
  ranks RANKOBS;
run;

proc sort data=rank1;
  by subject avisitn;
run;

data rankmi;
  set rank1;
  by subject avisitn;
  if last.subject;
run;

proc rank data=rankmi out=ADRANK nplus1 ties=mean;
  by avisitn;
  var RANKOBS;
  ranks Rankana;
run;

proc freq data = ADRANK;
  tables stratified vars*TRTP*Rankana / cmh2 scores = table;
run;

```

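### The fallback rank test for the co-primary endpoints is defined by two incompatible missing-data methods, and its CMH result has no pooling rule over the 30 imputations

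*SAP*

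**What the plan says.** SAP Section 6.1.2.2 describes an ANCOVA on multiply imputed data and adds a non-parametric analysis for the case where the residuals do not look normal. The lead-in is explicit about the data: "This supportive analysis will use the multiple imputation (MI) data at Week 12 using a non-parametric analysis of covariance". The quantity ranked is the residual from an ordinary least squares "regression with Week 12 MI response as a linear function of the baseline score". One result per endpoint is promised: "P-value for the between treatment comparison for each primary endpoint will be derived for the model".

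Five numbered steps follow as the method. Step 1 takes a different response, "The observed value of the primary endpoint (i.e., the last on treatment average number of daily micturition episodes"), and fits it on baseline at each visit. Step 2 ranks the residuals. Step 3 reads: "The standardized mid-rank from the last observation will be carried forward for missing values at week 12". Step 4 says "Standardized mid-ranks will be recalculated". Step 5 runs one stratified CMH mean score test.

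The example code ranks residuals by visit, sorts by subject and visit, keeps one record per subject with "if last.subject", ranks again by visit, and calls `PROC FREQ` with `cmh2`.

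Appendix 11.1 creates 30 completed datasets through Week 12. It fits the ANCOVA to each and pools an estimate and standard error in `PROC MIANALYZE`. It does not mention the rank test.

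**The concern.** One named test is given two ways of handling a missing Week 12 value. On the imputation reading, step 3 has nothing to act on. On the stepwise reading, the imputed data are never used. SAP Section 9 (changes from the protocol) and Appendix 11.1 do not say which applies. Protocol Section 9.4.4 does describe a CMH calculation per imputed dataset, but for the responder risk difference, and SAP Section 9.2 drops that analysis.

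If normality fails, this is the stated robustness check on both co-primary conclusions. Two programmers could each follow the section faithfully and report different p-values. Leaving the choice until after unblinding would also leave avoidable discretion over which one is reported.

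**Working it through.** **1. The two specifications side by side**

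| | Lead-in | Steps 1–5 |
|---|---|---|
| Response | Imputed Week 12 value | Observed value, fitted at each visit |
| Missing Week 12 | Filled 30 times | Last mid-rank carried forward |
| CMH tests | 30 | 1 |
| Single p-value | Needs a pooling rule; none given | Defined |

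**2. What the printed code does, by input**

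- *Observed data, all visits.* Nothing limits the input to Week 12, although the ANCOVA example in the same section does so. A completer's last record is then Week 24. The second `PROC RANK` also runs by visit on data sorted by subject. Once re-sorted, it ranks early leavers only among themselves, so step 4 is not done across subjects.
- *Observed data to Week 12.* The Week 24 problem goes; the separate ranking of leavers remains.
- *Thirty imputations stacked.* With no imputation index, one record per subject survives, so 1 of 30 imputations is used.
- *Each completed dataset to Week 12, in a loop.* The code gives a valid CMH test per dataset. Only pooling is missing: `cmh2` returns a chi-square and p-value, while Appendix 11.1 pools an estimate and a standard error.

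**3. The design figure**

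SAP Section 1.2.4 gives 462 evaluable per arm, difference 0.46, SD 1.972 and two-sided 0.05. SE = 1.972 × √(2/462) = 0.1298; 0.46/0.1298 − 1.96 = 1.585; power = 94.4% (stated 94.3%). The design inputs reproduce.

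**4. Size of the discrepancy (simulation)**

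- From the SAP: 544 per arm, SD 1.972, 15% lost before Week 12 (1088 × 0.15 ≈ 163 subjects), 30 imputations, three two-level stratification factors (8 strata).
- Assumed: exchangeable correlation of 0.4, 0.6 or 0.8 between Weeks 2, 4, 8 and 12; the same effect at every visit; monotone dropout at random after Week 2, 4 or 8; residuals normal, or lognormal with skewness about 1.4; true differences of 0.35 and 0.24.
- Imputation: sequential Bayesian regression on baseline and earlier visits with no treatment term, as in the printed Appendix 11.1 regression. Results were pooled by the rule given under the fix.
- Rank-LOCF: steps 1–5, with step 4 ranks taken across all subjects.
- 2000 trials per setting (1900 at 0.35).

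Ranges below are over the three correlations, in % of trials.

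| | 0.46 | 0.35 | 0.24 |
|---|---|---|---|
| Verdicts at 0.05 differ, normal residuals | 1.2–2.8 | 3.9–9.0 | 5.5–13.2 |
| Verdicts at 0.05 differ, skewed residuals | 0.2–1.1 | not run | 6.0–14.9 |
| The 30 p-values fall on both sides of 0.05, normal | 9–18 | not reported | 36–53 |

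Monte Carlo SE is about 0.5 points near 5%, 0.8 near 13% and 1.1 near 50%. Most disagreements are significant by rank-LOCF only: 8.0 of 8.9 points at 0.24 with correlation 0.6. Under the null, rejection is 4.2–5.3% (rank-LOCF), 4.1–5.3% (one imputation) and 2.1–4.2% (pooled imputations), so there is no type I error inflation.

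Smaller repeat runs at correlation 0.6 (200 to 600 trials) gave 1.8–3.5% disagreement at 0.46 and 6.7–10% at 0.24 or 0.25, consistent within simulation error. In the 200-trial run, ranking leavers only among themselves barely moved the rejection rate: 94.5% against 95.0% at 0.46, and 56.0% against 55.5% at 0.25.

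**5. Choice of pooling rule (normal residuals)**

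Compared with the rule proposed below, verdicts differ as follows.

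| Alternative | 0.46 | 0.24 |
|---|---|---|
| Combining the 30 chi-squares | at most 0.2% | at most 0.2% |
| Median of the 30 p-values | 0.5–1.2% | 1.8–5.3% |
| One imputation alone | 1.1–3.5% | 7.5–11.8% |

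**The case against.** The case on the other side has five parts.

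- **The SAP leans towards imputation.** The section title and lead-in both name it, and the code's dataset is called `rankmi`. Steps 1 and 3 may be leftover text. That is plausible, but the steps are presented as the method, so the contradiction has to be removed either way.
- **The code is a sketch.** It contains a placeholder for the stratification variables. The ANCOVA example also lacks an imputation index, and Appendix 11.1 supplies that loop. With the appendix's datasets, which stop at Week 12, the Week 24 and by-visit ranking problems disappear. This stands: those two defects apply only to observed-data input.
- **The pooling gap changes little if a sensible rule is used.** Combining chi-squares gives nearly the same verdicts as the proposed rule. The 36–53% figure describes 30 unpooled p-values, not changed conclusions. This also stands, but other simple choices do differ, and the SAP names none.
- **Part of the difference belongs to another issue.** The imputation regression has no treatment term. In a 1000-trial check at 0.24 (correlation 0.4/0.6/0.8), adding treatment cut disagreement from 12.4/8.6/6.0% to 9.8/7.1/5.1%. The excess of rank-LOCF rejections fell from 11.0/6.8/4.0 to 5.0/3.5/2.5 points. So about a fifth or less of the disagreement, but roughly 40–55% of the one-sided gap, comes from that omission.
- **The larger figures rest on effects that the documents do not give.** This is true; at the planned effect the disagreement is small.

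**Conclusion.** The point holds and is minor. The section is wrong as written: lead-in and steps prescribe incompatible methods, and on the imputation reading the promised single p-value is undefined. At the planned 0.46 the readings disagree in 1.2–2.8% of simulated trials with normal residuals, and in 0.2–1.1% with skewed residuals, the case in which this analysis would run. Disagreement reaches 5.5–14.9% at an assumed 0.24, where results are borderline and a robustness check matters most.

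These sizes depend on the assumed correlation, dropout pattern, residual shape and smaller effects. The 15% missing is an upper-end assumption: the FAS drops subjects with no post-baseline diary, and early-withdrawal visits can be slotted into a visit window, so real differences would be smaller. The textual conflict depends on none of this.

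The consequence is bounded. The analysis is supportive, runs only if normality fails, has no output in Table 9, and does not touch the MMRM, the imputation ANCOVA, the tipping point or the gatekeeping.

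**What to change.** Choose one method before unblinding and make text and code match.

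**If imputation is kept:** use the Appendix 11.1 datasets at Week 12 only, processed by imputation, with residuals ranked across all subjects. Reword step 1 to the imputed Week 12 value. Delete step 3, the last-record selection and the by-visit statements. State a pooling rule. One option uses T_h, E_h and V_h, the CMH observed sum, expected sum and variance in stratum h, and w_h = n_1h·n_0h/n_h:

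- D = Σ(T_h − E_h) / Σw_h
- SE = √(ΣV_h) / Σw_h

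Here (D/SE)² is the CMH mean score statistic for that dataset. D and SE are the pair that the existing `PROC MIANALYZE` step needs for Rubin's rules.

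**If carried-forward ranks are kept:** remove the imputation wording from the lead-in, limit the input to visits through Week 12, and drop the by-visit statement from the second `PROC RANK` so that step 4 ranks all subjects together.

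The cost is an edit to SAP text and example code. It needs no new data and no change to the primary analysis, and it can be checked in the blinded dry-runs already planned in SAP Section 2.2.

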6.1.2.3. MMRM with Stratification Factors as Observed

If more than 7% of subjects are misstratified, the co-primary MMRM efficacy analysis will be repeated using stratification factors as calculated from the baseline diary (baseline average number of daily micturition episodes, baseline incontinence) and prior medications (alpha blocker use with or without 5-ARI).

6.1.3. Subgroup Analysis

For following selected subgroups listed in [Section 4.1.3](#), a separate MMRM model will be fit on co-primary endpoints, respectively, based on the FAS.

- Alpha blocker use with or without 5-ARI (with vs. without, stratification factor as randomized)
- Baseline urinary incontinence (yes vs. no, stratification factor as randomized)
- Region (US vs. Non-US)
- Age category 2 (<65, \geq 65 years)
- Race (White, African American, Asian and Other)

The same model terms as used for the primary analysis specified in [Section 6.1.1](#) will be applied with additional terms for subgroup main effect, treatment by subgroup interaction, and treatment by subgroup by visit interaction. Only the estimate and p-value for the interaction term from the MMRM will be provided. With the exception of Age category 2 and Race subgroups, if less than 20% of randomized subjects are in a subgroup the corresponding subgroup analysis will not be performed. Descriptive summary statistics will be provided for all subgroups.

A forest plot will be provided to present the results from subgroup analyses. Side-by-side 95% confidence intervals will be plotted for each comparison to control within each subgroup, where the 95% confidence intervals are taken from the analysis table described above. The confidence intervals are stacked vertically on the page, with a reference line at zero for mean. All the subgroups should be plotted on a single figure (using multiple pages, if necessary).

The following subgroups will be used for descriptive statistics only: Age category 1, Age category 3, Prior anticholinergic, and Prior beta-3 agonist use.

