6.1. Co-Primary Endpoint Analysis

6.1.1. Primary Analysis

The primary analysis will be based on the FAS. Descriptive summary for observed and CFB will be provided by visit and treatment for both co-primary endpoints. Refer to parameter derivations from Bladder Diary data on Section 4.3.1.

Co-primary 1: CFB to Week 12 in average number of daily micturition episodes

For the assessment of difference between the treatment groups in change from baseline to Week 12 in average number of daily micturition episodes, a mixed model for repeated measures (MMRM) will be used incorporating on-treatment values at all time points (Weeks 2, 4, 8, 12, 16, 20, and 24). The model takes account of any correlation within the same subject over time by using all available data on the subjects. With the assumption of missing at random (MAR), this approach will provide unbiased estimates of treatment effects derived from the model.

The MMRM model will include terms for treatment, visit, baseline value (average number of daily micturition episodes), alpha blocker use with or without 5-ARI (with vs. without), baseline urinary incontinence (yes vs. no), region (US vs. non-US), and interaction of visit by treatment. Stratification factors as randomized will be used in the model. The Kenward-Roger adjustment will be used with restricted (or residual) maximum likelihood (REML) to make statistical inference. An unstructured covariance matrix will be used to model the correlation among repeated measurements. If the unstructured covariance model fails to converge with the default Newton-Raphson algorithm, the Fisher scoring algorithm will be used to provide initial values of the covariance parameters. In the rare event that none of the above methods yield convergence, the following structures will be investigated: heterogeneous Toeplitz, Toeplitz, heterogeneous First-Order Autoregressive [AR (1)], heterogeneous compound symmetry (HCS), and compound symmetry (CS). The covariance structure converging to the best fit, as determined by Akaike's information criterion (AIC), will be used.

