Primary inference will be drawn from the treatment difference between vibegron and placebo at Week 12. Results will be presented in terms of least square means (LSMEANS), treatment differences in LSMEANS, 95% confidence intervals for the treatment difference for all timepoints. Although nominal p-values for the treatment differences will be presented for all visits, the primary inference is at Week 12. The estimated LSMEANS (Standard Error (SE)) of CFB over time from the model will be plotted by treatment.

An example of the SAS code for the base procedure is given below:

```
proc mixed data = datain method = reml;
  class TRTP AVISITN USUBJID ALPHAB UI REGION;
  model CHG = TRTP AVISITN ALPHAB UI REGION BASE TRTP*AVISITN
    / ddfm=KR solution chisq;
  repeated AVISITN / subject=USUBJID type=UN r rcorr;
  lsmeans TRTP*AVISITN / pdiff=all cl alpha=0.05;
run;
```

Where TRTP is the planned treatment, AVISITN is the visit number, USUBJID is the unique subject identifier, ALPHAB indicates if the subject used 5-ARI in addition to alpha blockers at baseline, UI indicates baseline urinary incontinence, REGION indicates if the subject is in the United States or in the non-US countries and BASE indicates baseline value. The default Newton-Raphson algorithm is employed for type = UN. If the default algorithm fails to converge, use Fisher scoring algorithm to include option scoring = 5 in the model.

The normality assumptions for the primary analysis model will be assessed by inspection of the residuals from the model and normal probability plots. If assumptions of normality are not met, additional supportive analysis of the data will be performed in order to assess the robustness of the conclusions drawn from the primary analysis.

Co-primary 2: CFB to Week 12 average number of daily urgency episodes

The primary analysis will be identical to the analyses specified for the first co-primary described above with the addition of fitting in the categorical covariate of baseline average number of daily micturition episodes (≤ 12 vs. > 12 , stratification factor as randomized).

Multiplicity of Co-Primary Endpoints

No multiplicity adjustment is required for the co-primary endpoints since both endpoints need to be statistically significant at the 0.05 level in order to claim trial success.

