11.2.2. Output Figures

Table 10: List of Output Figures

Title	Population	Programming notes
Efficacy Endpoints		
14.2.1.1 Plot of LS Means (SE) of Change from Baseline in Average Number of Daily Micturition Episodes Primary Efficacy Analysis (MMRM)	FAS	Including all visits
14.2.1.2 Forest Plot of Vibegron Treatment Effect vs. Placebo on Average Number of Daily Micturition Episodes at Week 12 by Subgroup Primary Efficacy Analysis (MMRM)	FAS	
14.2.2.1 Plot of LS Means (SE) of Change from Baseline in Average Number of Daily Urgency Episodes Primary Efficacy Analysis (MMRM)	FAS	Including all visits
14.2.2.2 Forest Plot of Vibegron Treatment Effect vs. Placebo on Average Number of Daily Urgency Episodes at Week 12 by Subgroup Primary Efficacy Analysis (MMRM)	FAS	
14.2.3.1 Plot of LS Means (SE) of Change from Baseline in Average Number of Nocturia Episodes per Day (MMRM)	FAS	Including all visits
14.2.4.1 Plot of LS Means (SE) of Change from Baseline in Average Number of Daily Urge Urinary incontinence Episodes (MMRM)	FAS-I	Including all visits

Title	Population	Programming notes
14.2.5.1 Plot of LS Means (SE) of Change from Baseline in International Prostate Symptom Score (IPSS) Storage Score (MMRM)	FAS	Including all visits
14.2.6.1 Plot of LS Means (SE) of Change from Baseline in Volume Voided per Micturition (MMRM)	FAS	Including all visits
Safety Endpoints		
14.3.3.1 Scatter Plot of Maximum ALT Post-Baseline versus Maximum Total Bilirubin Expressed as Multiples of ULN	SAF	
14.3.3.2 Scatter Plot of Maximum AST Post-Baseline versus Maximum Total Bilirubin Expressed as Multiples of ULN	SAF	
14.3.3.3 Line Plot of Liver Chemistry Test Results over Time for Subjects with Elevated ALT or AST, and Elevated Total Bilirubin at Any Time	SAF	Only produce for subjects who potentially met Hy's law
14.3.4.1 Line Plot of Mean (SE) in CFB of Systolic Blood Pressure	SAF	X-axis starts from baseline visit
14.3.4.2 Line Plot of Mean (SE) in CFB of Diastolic Blood Pressure	SAF	X-axis starts from baseline visit
14.3.4.3 Line Plot of Mean (SE) in CFB of Pulse Rate	SAF	X-axis starts from baseline visit
14.3.5.1 Line Plot of Mean (SE) in Time-Matched Change from Day 1 of Orthostatic Systolic Blood Pressure	SAF-Orth	

Title	Population	Programming notes
14.3.5.2	Line Plot of Mean (SE) in Time-Matched Change from Day 1 of Orthostatic Diastolic Blood Pressure	SAF-Orth
14.3.5.3	Line Plot of Mean (SE) in Time-Matched Change from Day 1 of Orthostatic Pulse Rate	SAF-Orth

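### The subgroup MMRM in SAP 6.1.3 omits subgroup-by-visit and does not say which interaction is reported: one candidate p-value mixes in ordinary time trends, the other is not a Week 12 test

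*SAP*

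**What the plan says.** SAP 6.1.1 fits the primary MMRM "incorporating on-treatment values at all time points (Weeks 2, 4, 8, 12, 16, 20, and 24"), so there are seven visits. Its fixed effects end with "region (US vs. non-US), and interaction of visit by treatment", and the sample code agrees: "model CHG = TRTP AVISITN ALPHAB UI REGION BASE TRTP*AVISITN". Visit by treatment is the only interaction. The factors are declared by "class TRTP AVISITN USUBJID ALPHAB UI REGION". Primary inference is at Week 12.

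SAP 6.1.3 reuses those terms for five subgroup factors: 5-ARI use, baseline incontinence, region, age (two levels) and "Race (White, African American, Asian and Other"). It adds "additional terms for subgroup main effect, treatment by subgroup interaction, and treatment by subgroup by visit interaction". On output it says: "Only the estimate and p-value for the interaction term from the MMRM will be provided". It then takes the forest plot's 95% confidence intervals for the within-subgroup comparisons from that same table.

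The figure list in SAP 11.2.2 places the plot at Week 12: "Forest Plot of Vibegron Treatment Effect vs. Placebo on Average Number of Daily Micturition Episodes at Week 12 by Subgroup". There is a matching figure for urgency. The subgroup MMRM tables in SAP 11.2.1 (14.2.1.7 and 14.2.2.7) are to show all intervals, with Week 12 first. SAP 4.1.3 gives the purpose as checking whether the treatment effect is consistent across subgroups.

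**The concern.** When a three-way interaction is fitted without one of its component two-way terms, it takes over the missing term's degrees of freedom. Here the missing term is subgroup by visit. Suppose men on a 5-ARI, or men with incontinence, change over time differently from other men, but equally so in both arms. That is not treatment heterogeneity, yet the overall test of the three-way term would count it as evidence of an interaction.

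The plan adds two treatment-by-subgroup interactions and promises the result of one, unnamed. A programmer could report either and comply with the text, and the choice could be made after unblinding. The three-way p-value can mislead. The two-way p-value concerns the average over Weeks 2 to 24, not Week 12. At stake is the credibility of the consistency check, not the primary result.

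**Working it through.** **Inputs from the documents.** Two arms; seven visits; two-level subgroups, and race with four levels; 462 evaluable men per arm (924 in total), SD 1.972, difference 0.46, two-sided 0.05 (SAP 1.2.4). The documents give no error rate for the subgroup interaction. The plan's own power figures were reproduced to confirm N, SD and alpha: about 94.4% for micturitions (stated 94.3%) and 90.0% for urgency (stated 90%).

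**Degrees of freedom, two-level subgroup.** There are 2 × 2 × 7 = 28 treatment-by-subgroup-by-visit cells. Apart from the other covariates, the terms without the three-way use:
- intercept 1, treatment 1, visit 6, treatment by visit 6, subgroup 1, treatment by subgroup 1: total 16.

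The three-way term takes the remaining 28 − 16 = 12. With subgroup by visit in the model (6 df) it takes 28 − 22 = 6. So half of the 12-df test is the omitted subgroup-by-visit effect. For race there are 2 × 4 × 7 = 56 cells; the other terms use 1 + 1 + 6 + 6 + 3 + 3 = 20, leaving 36, of which 18 are subgroup by visit. The ranks of the CLASS-coded design matrices confirm all four figures.

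**What the 12-df test tests.** Its null hypothesis is no subgroup-by-visit effect in either arm, which is stricter than equal subgroup-by-visit effects in the two arms.

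**Size of the effect.** Assumptions not in the documents: no treatment heterogeneity; a subgroup drift linear in weeks from Week 2 to Week 24, identical in both arms; the correlation structure; the subgroup split; complete data on all 924 men at every visit.

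With exchangeable correlation ρ and subgroup share p, the noncentrality is

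λ = 2 × 462 × p(1 − p) × drift² × S / [SD² × (1 − ρ)],

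where S is the sum of squared deviations of (week − 2)/22 over the seven visits, S = 0.8335. For p = 0.5 and ρ = 0.5:
- drift 0.2: λ = 231 × 0.04 × 0.8335 / (3.889 × 0.5) = 3.96
- drift 0.3: λ = 231 × 0.09 × 0.8335 / (3.889 × 0.5) = 8.91

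Rejection is the probability that a noncentral chi-square on 12 df exceeds 21.03. AR(1) rows use the same quadratic form with that covariance matrix.

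| Split | Correlation | Drift 0.2 | Drift 0.3 |
|---|---|---|---|
| 50:50 | exchangeable 0.5 | 20% | 45% |
| 50:50 | exchangeable 0.7 | 33% | 72% |
| 50:50 | AR(1) 0.8 | 10% | 19% |
| 20:80 | exchangeable 0.5 | 13% | 28% |
| 20:80 | AR(1) 0.8 | 8% | 13% |

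**Simulation check.** This used 2,000 trials per setting, an estimated unstructured covariance and a constant treatment effect of −0.46. For a 50:50 split with exchangeable 0.5, exchangeable 0.7 or AR(1) 0.8, the 12-df test rejected about 5% with no drift, 13% to 51% at drift 0.25, and 53% to nearly 100% at drift 0.5. Over all settings, which also included a 20:80 split:
- three-way test with subgroup by visit added (6 df): 4.2% to 6.0%
- two-way treatment-by-subgroup test in the SAP's model: 4.4% to 6.0%
- Week 12 treatment-by-subgroup contrast in the SAP's model: 3.6% to 6.1%

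Mean estimates of the last two were within 0.02 of zero. The reason is that under CLASS coding the three-way term already saturates all 28 cells. Adding subgroup by visit reparameterises the model and leaves fitted values, LS means and the Week 12 contrast unchanged.

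**The case against.** The strongest reply is that the SAP never says the overall three-way test is the one reported. It promises an estimate with a p-value, and a 12-df test has no single estimate, so the two-way term or a Week 12 contrast fits the wording better, at least for two-level factors. Both are uncontaminated. This stands: a reader might infer that the plan's interaction test will flag ordinary time trends, but the documents support that only if the three-way p-value is chosen.

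A reader might also infer that the omission biases the subgroup estimates. It does not under the SAP's CLASS statement. Bias would need hand-coded product terms, which the SAP does not show. In that case a 0.5 drift at exchangeable correlation 0.6 shifts the treatment-by-subgroup contrast by about −0.23 at Week 2 and +0.27 at Week 24, but only about −0.01 at Week 12.

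The Week 12 output is largely planned already, through the subgroup tables and forest plots, so the conflict over confidence intervals is one of wording inside 6.1.3. The drift and correlations are assumed, the AR(1) figures are much lower than the exchangeable ones, and 924 is the number evaluable at Week 12, not a complete set to Week 24.

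Finally, the subgroup analyses are supportive. SAP 4.1.2 confines multiplicity control to the co-primary and key secondary hypotheses, SAP 1.2.4.1 disclaims formal testing in the BPH-treatment subgroups, and Protocol 9.4.4.1 makes subgroup analyses optional.

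These points limit the size of the problem but do not remove it. The text still permits a misleading p-value; the two-way alternative averages over seven visits; and for race neither interaction term has a single estimate.

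**Conclusion.** Wrong as written, but minor, because the analysis is supportive. The subgroup-by-visit term is missing and the reported interaction is not named. If the overall three-way p-value is used, its false-rejection rate rises from 5% to about 20% or 45% (exchangeable 0.5), or about 10% or 19% (AR(1) 0.8), for a shared drift of 0.2 or 0.3 episodes in a 50:50 subgroup. These rates rest on the assumed linear drift, correlation and complete data, and they do not apply if another term is reported. If the two-way p-value is used, it is valid but answers a question about the average over all visits. The documents do not support a claim of biased subgroup estimates under the SAP's coding, or of any effect on the co-primary or secondary conclusions. The degrees-of-freedom result needs none of these assumptions.

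**What to change.** In SAP 6.1.3:

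1. Name the Week 12 treatment-by-subgroup contrast as the reported interaction test: 1 df for two-level factors, 3 df for race. For race, say that the test is joint and has no single estimate.
2. Add subgroup by visit, so that any three-way test shown is a true three-way test (6 df, or 18 for race).
3. Replace the sentence limiting output to the interaction result. State that the table also gives the Week 12 LS-mean difference and 95% confidence interval within each subgroup level, and that these feed the forest plot.

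The cost is one model term, a few contrast and estimate statements, and a reworded sentence. No new data are needed. Item 2 leaves the estimates unchanged; item 1 matters most, because it settles the test before unblinding.
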